**Table 6. Summary of Abrocitinib Oral Suspension Formulations to be administered for PK and Taste Assessment**

Formulation	CCI		Supply	Use
1	CCI		Provided by Pfizer Pharmaceutical Sciences DMID D1900119 Abrocitinib 25 mg/mL Oral Suspension in 75 mL HDPE bottle (60 mL)	PK + Taste Evaluation
2	CCI		Provided by Pfizer Pharmaceutical Sciences Provided by Pfizer Pharmaceutical Sciences DMID D1900120 Abrocitinib 25 mg/mL Oral Suspension in 75 mL HDPE bottle (60 mL, without flavour)	Taste Evaluation only
3	CCI		Prepared at CRU	
4	CCI		Prepared at CRU	
5		CCI	Prepared at CRU	
6		CCI	Prepared at CRU	

### 6.1.1. Administration

**Part A:** Following an overnight fast of at least 10 hours, participants will receive the study intervention, abrocitinib, at approximately 0800 hours (plus or minus 2 hours). Investigator site personnel will administer the study intervention during each period with ambient temperature water to a total volume of approximately 240 mL. Participants will swallow the study intervention whole and will not manipulate or chew the study intervention prior to swallowing. For participants receiving the ARA, famotidine, a 40 mg dose of famotidine tablet will be administered 2 hours before administering the study intervention, abrocitinib, with participants fasting for at least 10 hours before taking abrocitinib.

**Part B:** Abrocitinib oral suspension formulations 1 to 6 for tasting will be offered to all participants in a blinded fashion. Following an overnight fast of at least 10 hours, participants will receive the study intervention, abrocitinib, at approximately 0800 hours (plus or minus 2 hours). Participants will place samples into their mouths, swish the sample in the mouth for approximately 10 seconds and then swallow it. Each participant will record the sensory attributes at timed intervals of 0 (immediately after dosing), 5, 10 and 20 minutes after swallowing using the Abrocitinib Taste Assessment Questionnaire. Each formulation will be tested daily. Participants will be asked as much as possible to not verbalize their responses and not discuss taste with other participants until after they have filled out the response for that formulation in the questionnaire. Participants will cleanse their mouth with room temperature water before tasting a formulation. This water will not be swallowed. For participants receiving the ARA, famotidine, a 40 mg dose of famotidine tablet will be administered 2 hours before administering the study intervention with participants fasting for at least 10 hours before taking abrocitinib.

For both Part A and Part B of the study, participants will be instructed to fast for at least 10 hours before receiving abrocitinib. Water will be withheld for 1-hour predose and 1 hour after study treatment administration, and food will only be allowed after 4 hours postdose.

In order to standardize the conditions throughout the study, all participants will be required to refrain from lying down (except when required for BP, pulse rate, and ECG measurements), eating, and drinking beverages other than water during the first 4 hours after dosing.

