- k. Review taste questionnaire and instructions with participants prior to the first taste assessment on Period 4, Day 1. Each participant will record the sensory attributes at timed intervals of 0 (immediately after dosing), 5, 10 and 20 minutes after swallowing the suspension, using a Taste Assessment Questionnaire (see [Appendix 8](#)).

C  
C  
I

CC1

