**Table 4. Randomized Treatment Sequences of Part A**

Sequence	Period 1	Period 2	Period 3
1 (n=3)	A	B	C
2 (n=3)	B	C	A
3 (n=3)	C	A	B
4 (n=3)	A	C	B
5 (n=3)	B	A	C
6 (n=3)	C	B	A

Treatment A = Abrocitinib 200 mg commercial tablet only, under fasted conditions.

Treatment B = Abrocitinib 200 mg oral suspension formulation 1, under fasted conditions.

Treatment C = Famotidine 40 mg tablet administered 2 hours prior to abrocitinib 200 mg commercial tablet under fasted conditions.

Healthy participants will be screened within 28 days prior to the first administration of the study intervention to confirm that they meet the participant selection criteria for the study. Eligible participants will be admitted to the CRU on Day -1 and will be confined in the CRU until Discharge, which is Day 2 of Period 9, in Part B of the study (SoA), after completing both Parts A and B of the study. Day -1 is defined as the day prior to the first day of dosing (Day 1).

In Period 1 through Period 3 of Part A, participants will receive a single 200 mg dose of abrocitinib commercial tablet (Treatment A), a single 200 mg dose of abrocitinib oral suspension (Treatment B), or 40 mg famotidine tablet administered 120 minutes prior to a single dose of 200 mg dose of abrocitinib commercial tablet (Treatment C) after a fast of at least 10 hours before taking the study intervention, abrocitinib. All participants will be fasting for at least 10 hours before taking abrocitinib. CCI

CCI

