**Table 5. Randomized Treatment Sequences of Part B**

Sequence	Period 4	Period 5	Period 6	Period 7	Period 8	Period 9
1 (n=3)	F1+ARA	F2+ARA	F3+ARA	F4+ARA	F5+ARA	F6+ARA
2 (n=3)	F6+ARA	F1+ARA	F2+ARA	F3+ARA	F4+ARA	F5+ARA
3 (n=3)	F5+ARA	F6+ARA	F1+ARA	F2+ARA	F3+ARA	F4+ARA
4 (n=3)	F4	F5	F6	F1	F2	F3
5 (n=3)	F3	F4	F5	F6	F1	F2
6 (n=3)	F2	F3	F4	F5	F6	F1

F1 = Abrocitinib oral suspension formulation 1 under fasted conditions.

F2 = Abrocitinib oral suspension formulation 2 under fasted conditions.

F3 = Abrocitinib oral suspension formulation 3 under fasted conditions.

F4 = Abrocitinib oral suspension formulation 4 under fasted conditions.

F5 = Abrocitinib oral suspension formulation 5 under fasted conditions.

F6 = Abrocitinib oral suspension formulation 6 under fasted conditions.

ARA = Famotidine 40 mg under fasted condition.

For any new healthy participants joining Part B only to support the achievement of the total number of 18 healthy participants enrolled or randomized in this part of the study, screening for healthy participants will be performed within 28 days prior to the first administration of the study intervention to confirm that they meet the participant selection criteria for the study.

Abrocitinib oral suspension formulations 1 to 6 for tasting will be offered to all participants in a blinded fashion. Participants randomized to Sequence 1-3 will receive famotidine (40 mg with 240 mL of room temperature water) 120 minutes before administering a single 200 mg dose of abrocitinib oral suspension formulations 1 to 6 with participants fasting for at least 10 hours before taking abrocitinib. While participants randomized to Sequence 4-6 will receive abrocitinib oral suspension formulations 1 to 6 with participants fasting for at least 10 hours before taking abrocitinib.

For participants receiving the ARA, famotidine, a 40 mg dose of famotidine tablet will be administered 2 hours before administering the study intervention with participants fasting for at least 10 hours before taking abrocitinib.

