New participants enrolled in Part B only will be admitted to the CRU on Day -1 and will be confined in the CRU until Discharge, which is Day 2 of Period 9. On Day 1 of each treatment period under fasted conditions, participants will receive famotidine tablet (40 mg with 240 mL of room temperature water) administered 120 minutes before a single 200 mg dose of abrocitinib oral suspensions (Formulations 1 to 6) or administered a single 200 mg dose of abrocitinib oral suspension alone (Formulations 1 to 6), after a fast of at least 10 hours before abrocitinib administration.

For a participant who completes both Part A and Part B of the study, the expected duration of participation from screening in Part A to the follow-up telephone contact in Part B of the study is approximately 11 weeks. While for a participant who completes only Part A or Part B of the study, the expected duration of participation from screening to the follow-up telephone contact is approximately 10 weeks. Participants who discontinue from the study may be replaced at the sponsor's discretion. The replacement participant will receive the same treatment sequences as the participant who discontinued.

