inhibitor of H2 receptors which inhibits both basal and nocturnal gastric secretion. After oral administration of famotidine, the onset of the antisecretory effect occurred within 1 hour; the maximum effect was dose-dependent, occurring within 1 to 3 hours. Intragastric pH after a single dose of famotidine 40 mg was shown to rapidly increase to pH >4.0 within 2 hours of administration, with a duration of inhibition of secretion lasting for 10 to 12 hours. In the present study, the maximum allowed dose of famotidine, famotidine 40 mg, will be administered 2 hours before abrocitinib to achieve its maximal acid-reducing and pH-increasing effects. This dose was selected to align with the FDA guidance stating that sponsors should select the maximum recommended dose of an ARA to characterize the worst-case scenario possible.

**Part B:** In Part B, treatments will be presented to the participants in a blinded fashion to minimize the potential bias for taste evaluation.

CCI

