#### **6.1. Study Intervention(s) Administered**

For this study, commercial tablet formulation of abrocitinib 200 mg tablet, 6 oral suspension formulations of abrocitinib and famotidine 40 mg tablets will be administered. Commercial

tablet of abrocitinib 200 mg for oral administration will be supplied to the CRU as packaged bulk bottles and labeled according to local regulatory requirements. The packaged bulk bottles will be provided to the site for dispensing by the pharmacy.

Abrocitinib 25 mg/mL oral suspension will be supplied as a white to off-white ready to use suspension, packaged in a 75 mL HDPE white, round bottle with a heat induction seal and white child resistant cap. Each bottle of abrocitinib will contain 60 mL of oral suspension. As part of a rBA in Part A and taste assessment study in Part B, 25 mg/mL suspensions of abrocitinib will be dosed to participants. Six suspension formulations will be evaluated in the study, the first suspension formulation (Formulation 1) will be used for PK assessment, in Part A of the study, and taste evaluation, in Part B of the study. While, the 5 others (Formulation 2-6) will be used only in Part B of the study for taste evaluation only as outlined in [Table 6](#).

Famotidine 40 mg tablets will be supplied by the CRU.

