**10.8. Appendix 8: Taste Assessment Questionnaire**

1. Questionnaire should be administered to adult participants, preferably by the trained staff. The clinical staff is trained by the CRU clinical coordinator for performing the taste questionnaire and regarding the specific study restrictions.
2. Use colored copy of the questionnaire.
3. Do not alter (reduce or enlarge) the original size of the questionnaire.
4. Please gather the following background information:

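### As most naturally read, the Part B no-discussion request ends while other participants have yet to rate the same formulation; a low-priority wording change would close the gap.

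*Protocol*

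**What the plan says.** Protocol 6.1.1 (Part B), and the synopsis in 1.1 in almost the same words, ask participants as far as possible to keep their responses to themselves and to "not discuss taste with other participants until after they have filled out the response for that formulation in the questionnaire". Responses are recorded at 0, 5, 10 and 20 minutes after swallowing, with one formulation per participant per day.

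Table 5 in Protocol 4.1 sets out six sequences of three participants over Periods 4 to 9. Participants continuing from Part A are "confined in the CRU until Discharge, which is Day 2 of Period 9, in Part B of the study"; those joining for Part B only are likewise "confined in the CRU until Discharge, which is Day 2 of Period 9".

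Protocol 4.2 gives the reason for blinding: "treatments will be presented to the participants in a blinded fashion to minimize the potential bias for taste evaluation".

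Two other places touch on instructions. Table 2, footnote k, reads: "Review taste questionnaire and instructions with participants prior to the first taste assessment on Period 4, Day 1". Appendix 8 has clinic staff trained for "performing the taste questionnaire and regarding the specific study restrictions". Neither states a longer restriction on discussion, and no other visible text does.

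**The concern.** The Part B primary measures are subjective marks on a colour bar. Blinding hides which formulation is in the cup. It does not stop one participant from telling another what a sample tasted like. The no-discussion request is the safeguard against that, so the moment at which it ends matters.

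If it ends once a participant has completed their own response, that participant is free to talk about 20 minutes after swallowing, while most of the others have still to taste the same suspension. Remarks heard beforehand could shape expectations or the way the scale is used. The scores are meant to guide the choice of a pediatric formulation and to inform whether taste masking is needed. The planned summaries (means, 90% CIs, radar plots and boxplots) would not detect or adjust for shared impressions.

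**Working it through.** **Inputs.** Table 5 (six sequences, n=3 each, Periods 4 to 9); the 18 participants stated for Part B in Protocol 4.1; questionnaire times to 20 minutes and dosing at about 0800 plus or minus 2 hours (Protocol 6.1.1).

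**1. The plan's own count.** 6 × 3 = 18, as stated. Counting one rating per participant per formulation, there are 18 × 6 = 108 ratings.

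**2. Who has still to rate.** Every period of Table 5 contains all six formulations, each in exactly one sequence. Three participants therefore rate a given formulation each day, and 18 − 3k have yet to rate it after k periods:

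| After Period | 4 | 5 | 6 | 7 | 8 | 9 |
|---|---|---|---|---|---|---|
| Yet to rate each formulation | 15 | 12 | 9 | 6 | 3 | 0 |

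**3. Later-day ratings, all six sequences resident together.** Per formulation, 18 − 3 = 15 ratings come on a later day than another sequence's rating. Over six formulations, 15 × 6 = 90 of 108 (83%). Formulation 1 "will be used for PK assessment, in Part A of the study, and taste evaluation, in Part B of the study", so Part A completers have met it before. Leaving it out gives 15 × 5 = 75 of 18 × 5 = 90, also 83%.

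**4. Fewer sequences together.** With m resident sequences the later-day share is (3m − 3)/3m = (m − 1)/m:
- m = 1: 0 of 18
- m = 2: 18 of 36 (50%)
- m = 3: 36 of 54 (67%)
- m = 6: 90 of 108 (83%)

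**5. Same-day contact, not counted above.** The dosing window runs from 0600 to 1000 and the questionnaire ends at 20 minutes. The first of three participants in a sequence could finish before the other two are dosed. In that extreme case a single sequence gives 2 × 6 = 12 of 18 (67%), and all six give (15 + 2) × 6 = 102 of 108 (94%). The figures in steps 3 and 4 are therefore not upper bounds, and mixing of sequences is not strictly required. The order of dosing within a day is not stated.

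**6. With the changed end point.** If the request is kept, no rating would follow another participant's release to discuss that formulation with someone who has still to rate it: 0 of 108. Sample size and analysis are unaffected.

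**The case against.** The strongest reply is that the sentence need not mean what is feared. The nearest antecedent of 'they' is the other participants. On that reading the listener must already have rated the formulation, and there is no gap. This stands as a genuine ambiguity. It does not remove the case for a change, since a sentence that protects the ratings on one reading and not on another should be made explicit.

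Second, the documents do not say that participants are housed or dosed together. Confinement dates fix the length of stay, not the company, and Protocol 8 refers to earlier and subsequent groups. Text after the Part B rationale in 4.2 is redacted, and the site's instructions are not shown. All of this stands, so a gap in actual conduct is not established.

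Third, blinding makes it hard to tie a remark to a later sample, and exposure is equal across formulations when sequences are equally represented. This limits the likely harm. It is not complete protection: Table 5 is cyclic, so in Periods 5 to 9 each sequence receives the suspension that one other sequence had the day before, a constant lag that participants comparing notes could notice. Nothing shows that anyone would.

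Fourth, the results are descriptive (Protocol 9.3.2.1.2; SAP 8.2) and SAP 4.2 has no decision rules. This supports a low priority.

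**Conclusion.** The point holds as a cheap improvement of low priority. On the natural reading, the request releases a participant while up to 15 of 18 others have yet to rate that formulation. If all six sequences are resident together, 90 of 108 ratings fall on a later day than another sequence's rating of the same formulation.

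This rests on two assumptions: that 'they' means each participant's own response, and that participants are in contact during confinement. The documents settle neither.

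A reader might infer that 83% of the taste scores are contaminated, or that 83% is the most that could be affected. The documents support neither inference. The count describes tasting order. It shows no conversation, and gives no direction or size for any effect. It also omits same-day contact, which could take the count to 102 of 108. Nor can one infer that the trial was run without a longer restriction, because redacted text or site instructions may contain one.

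**What to change.** In Protocol 1.1 and 6.1.1, replace the end of the request with: *until they have been discharged after Period 9, and not with any participant who has yet to complete their last Part B questionnaire*. Include the same sentence in the instruction review under Table 2, footnote k.

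The second half of the clause makes the identity of 'they' immaterial. It also covers contact with replacements and Part B-only joiners admitted later.

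The cost is one clause in two places and one line in a review that is already scheduled. The downsides are a longer restriction during confinement and possible IRB/EC review under Protocol 10.1.1, which does not settle whether such a clause counts as a change to study design. The request remains best-effort, so its benefit depends on voluntary adherence. Dosing, assessments, participant numbers and analysis do not change. If site instructions already carry a longer restriction, aligning the protocol wording with them is enough.

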### 6.2. Preparation, Handling, Storage, and Accountability

1. The investigator or designee must confirm appropriate temperature conditions have been maintained during transit for all study interventions received and any discrepancies are reported and resolved before use of the study intervention.
2. Only participants enrolled in the study may receive study intervention and only authorized site staff may supply or administer study intervention. All study interventions must be stored in a secure, environmentally controlled, and monitored (manual or automated recording) area in accordance with the labeled storage conditions with access limited to the investigator and authorized site staff. At a minimum, daily minimum and maximum temperatures for all site storage locations must be documented and available upon request. Data for nonworking days must

indicate the minimum and maximum temperatures since previously documented for all site storage locations upon return to business.

3. Any excursions from the study intervention label storage conditions should be reported to Pfizer upon discovery along with any actions taken. The site should actively pursue options for returning the study intervention to the storage conditions described in the labeling, as soon as possible. Once an excursion is identified, the study intervention must be quarantined and not used until Pfizer provides permission to use the study intervention. Specific details regarding the definition of an excursion and information the site should report for each excursion will be provided to the site in the PCRU local/site procedures.
4. Any storage conditions stated in the SRSD will be superseded by the storage conditions stated on the label.
5. Study interventions should be stored in their original containers.
6. See the DAI for storage conditions of the study intervention once reconstituted.
7. The investigator, institution, or the head of the medical institution (where applicable) is responsible for study intervention accountability, reconciliation, and record maintenance (ie, receipt, reconciliation, and final disposition records), such as the IPAL or sponsor-approved equivalent. All study interventions will be accounted for using a study intervention accountability form/record.
8. Further guidance and information for the final disposition of unused study interventions are provided in the PCRU local/site procedures. All destruction must be adequately documented. If destruction is authorized to take place at the investigator site, the investigator must ensure that the materials are destroyed in compliance with applicable environmental regulations, institutional policy, and any special instructions provided by Pfizer.

Upon identification of a product complaint, notify the sponsor within 1 business day of discovery.

### **6.2.1. Preparation and Dispensing**

Within this protocol, preparation refers to the investigator site activities performed to make the study intervention ready for administration or dispensing to the participant by qualified staff. Dispensing is defined as the provision of study intervention, concomitant treatments, and accompanying information by qualified staff member(s) to a healthcare provider, or to a participant in accordance with this protocol. Local health authority regulations or investigator site guidelines may use alternative terms for these activities.

Abrocitinib tablets will be dispensed at the CRU in the individual dosing containers by 2 operators, one of whom is an appropriately qualified and experienced member of the study staff (eg, physician, nurse, physician's assistant, nurse practitioner, pharmacy

assistant/technician, or pharmacist). The tablets will be provided in unit dose containers and labeled in accordance with Pfizer regulations and the clinical site's labeling requirements.

For the oral suspension formulations of abrocitinib, see the DAI for instructions on how to prepare the study intervention for administration. Study intervention should be prepared and dispensed by an appropriately qualified and experienced member of the study staff (eg, physician, nurse, physician's assistant, nurse practitioner, pharmacy assistant/technician, or pharmacist) as allowed by local, state, and institutional guidance. A second staff member will verify the dispensing.

The handling of famotidine tablets should be according to the product package insert.

### **6.3. Measures to Minimize Bias: Randomization and Blinding**

#### **6.3.1. Allocation to Study Intervention**

The investigator's knowledge of the treatment should not influence the decision to enroll a particular participant or affect the order in which participants are enrolled.

The investigator, or delegated staff, will assign participant numbers to the participants as they are screened for the study. Pfizer will provide a randomization schedule to the investigator and, in accordance with the randomization numbers, the participant will receive the study treatment regimen assigned to the corresponding randomization number.

